5.2 Subject Population

The study population will consist of those volunteers from the HIV clinics at the participating military HIV treatment centers including NMCSD, WRNMMC, SAMHS, and NMCP in their respective catchment areas. Each clinic has approximately 500 HIV-positive patients at any one time. Since all adult HIV patients are eligible who do not have allergies to the agents utilized in this study (mupirocin (Bactroban®) nasal ointment or hexachlorophene (pHisoHex®) soaps), who are not healthcare workers with direct patient contact, and who are not pregnant or breastfeeding, over 95% of clinic patients will be eligible for enrollment. A history of prior MRSA colonization and/or infection does not exclude entry into this study. The total population of the study will be 550 participants. If approximately 10-15% of participants carry the bacteria MRSA, then approximately 38 patients will receive topical antibacterial treatment and the other 38 will receive placebo. Enrollment will be on a continuous basis until 550 participants have been enrolled. The number of subjects per site will vary. The San Antonio Military Medical Center will only enroll patients that reside locally to their medical treatment facility. For the retrospective cohort, the study population will consist of all HIV patients who are 18 years or older and followed in the NMCSD HIV clinic.

5.3 Inclusion Criteria

1. Adults (≥ 18 years of age) who are HIV positive by a reactive screening (ELISA, EIA) and a confirmatory test (Western blot) and who are able to attend the study visits which are every 6 months ($+- 2$ months), at the minimum.

5.4 Exclusion Criteria

1. Known allergy to mupirocin (Bactroban®) nasal ointment or hexachlorophene (pHisoHex®) soaps or constituents of these products.
2. Age less than 18 years.
3. Inability to remain in the study for the two year duration.
4. Pregnant or breastfeeding females.
5. Females who intend to become pregnant during the two year study time period.
6. Persons who are healthcare providers with direct patient contact.

For the study evaluating medical records for the incidence and risk factors of MRSA infections, all adult HIV patients in the NMCSD HIV clinic will be evaluated.

VI. METHODS

6.1 Pre-enrollment

During regularly scheduled medical visits, HIV-positive patients will be offered participation in this research study. Eligibility requirements will be assessed through verbal discussion. IRB approved advertisement posters about the study will be posted in the clinic. Supplies for the study and subsequent data collection will be organized. Study staff jobs will be allocated to allow for optimal study performance during enrollment and data collection. The case report forms (CRFs) will be created to ensure consistent reporting and time efficiency.

6.2 Enrollment

The purpose of the trial, the entailed procedures, and the potential risks and benefits will be explained in person. Those who agree to the study will complete an informed consent process with the study coordinator and/or study physician, at which time it will be verbally verified that the subject comprehends the purpose of the trial, and the risks and benefits of participating. The subject will be provided adequate time to read the consent and to ask questions about the study. The subject will be offered a signed copy of the informed consent and a copy will be filed in the patient's medical record. The signed original consent form will be stored confidentially according to site IRB requirements. Patients who meet the inclusion criteria will be consented, registered at DCC, assigned a PIN and study identification number (refer to section 5.1), and enrolled into the study.

6.3 Active Surveillance & Clinic Assessments

Each study participant will be seen a minimum of five times over the 24-month study period by a study physician or study team member at the clinic (baseline visit and every six months (+/- 2 months) for a two year period). The maximum number of visits depends on if the patient has repeated infections or colonization for MRSA; this will likely not exceed 12 visits during the 2 year study period. This includes Visit 1 to sign the informed consent and register subject with DCC (assigned a PIN). Women of childbearing age will undergo a urine pregnancy test to assure that she meets inclusion/exclusion criteria. Enrolled patients will fill out questionnaires including data on prior MRSA or soft tissue infections, recent hospitalizations, demographic information (age, race, sex), substance use (alcohol, tobacco and illicit drugs), current and recent (within the past 12 months) antibiotics, current receipt of highly active antiretroviral therapy (HAART), contact with persons with a history of soft tissue infections and/or MRSA, relative or contact who works in the healthcare setting, exercise habits, sexual activities, sexually transmitted diseases, and activities previously associated with MRSA including sports, use of public baths/saunas, and hygienic practices (refer to case report forms). Each participant will have swabs of their nares, throat, axilla, groin, and perirectal area obtained for determining MRSA or MSSA colonization. Study coordinators will examine the patient's medical records and the hospital computer database for medication use, medical conditions including MRSA or soft tissue infections, hospitalizations, sexually transmitted diseases, and HIV data including CD4 count, HIV viral loads, and CDC staging.

During regular study visits 2, 3, 4, and 5, patients will have repeated swabs, questionnaires and review of their medical record which occurs every six months (+/- 2 months). The study duration for each participant is 24 months.

Patients will have the following swabs to detect colonization of MRSA or MSSA performed:

[figure not shown]
- one swab of both nares;
- one swab of the throat
- one swab of the bilateral groin areas;
- one swab of the axilla areas; and
- one swab of the perirectal area.

Patients will be evaluated at 6, 12, 18, and 24 study months (\pm 2 months) for repeat swabs (1. one swab of both nares; 2. one swab of the throat; 3. one swab of the bilateral groin areas; 4. one swab of the axilla areas; and 5. one swab of the perirectal area). Patients will also complete questionnaires regarding recent antibiotic use, recent soft tissue infections, recent sexually transmitted diseases, hospitalizations, substance use, sexual activities, and activities previously associated with MRSA (refer to case report forms). Study coordinators will search the patient's medical records and the hospital computer database for medication use, medical conditions including MRSA or soft tissue infections, hospitalizations, sexually transmitted diseases, and HIV data including CD4 count, viral loads, and CDC staging.

Culture results regarding MRSA carriage are to be finalized within 3-4 days of collection. Patients found to have a positive culture for MRSA during the study period from the colonization swabs will be randomized in a 1:1 double-blinded fashion to mupirocin (Bactroban®) nasal ointment twice daily for seven days plus hexachlorophene (pHisoHex®) washes with showering once daily for seven days or to a placebo nasal ointment (white petroleum) and a placebo body soap with no antimicrobial activity for seven days. The patient will be randomized within 7 days of the receipt of the MRSA positive culture result. Women of childbearing age will have a urine pregnancy test to assure they are not pregnant before dispensing of these medications; women found to have a positive pregnancy will be terminated from the study.

Patients who are colonized with MRSA and who reside locally to the medical treatment facility and are able to return to the clinic will have repeat swabs (five swabs from sites listed above) every month (+/- 7 days). A month will be specifically defined as 28 days. Those who have repeat positive colonization swabs during this initial 6 month follow-up period will be observed. This data will assess the efficacy of decolonization procedures on MRSA carriage rates. Patients who are not local to the clinic will not have these repeat swabs performed, but rather will be seen at the next scheduled 6 month study visit. Adherence to the study medications will be assessed at the next scheduled study visit by a patient questionnaire (refer to case report forms). Each time a patient has a positive isolate for MRSA or MSSA, this will be frozen and saved for molecular analysis to determine the most common molecular types colonizing HIV patients and to determine if patients acquire new strains or remain colonized with the same strain over time.

All study patients (both those initially found to be colonized with MRSA and those with negative colonization swabs) will be re-evaluated in six month intervals ($+/- 2$ months) until the end of the study. Patients found to be positive at these subsequent 6 month intervals, will be randomized again, treated and followed as described above. During the last study visit (at the 2-year time period), patients will have swabs, but not undergo randomization. Hence, every 6 months, patients positive during that visit for MRSA colonization will be re-randomized in a 1:1 double-blinded fashion to mupirocin (Bactroban®) nasal ointment twice daily for seven days plus hexachlorophene (pHisoHex®) washes with showering once daily for seven days or to a placebo nasal ointment (white petroleum) and a placebo body soap with no antimicrobial activity for seven days. Repeat randomization will occur every 6 months for those carrying MRSA. For example, some patients initially randomized to receive Bactroban® and pHisoHex®, may later be randomized to the placebo arm, and vice versa.

Begin at the top of diagram again every 6 months ($+/- 2$ months). If patient is found to be positive on swabs, they are re-randomized to one of the two treatment groups for every 6-month positive swab.

Patients will be asked to report to their enrolling HIV clinic for any soft tissue infections or any infection thought to be secondary to MRSA; if able, cultures of the wound site will be obtained. Blood cultures will be obtained at the primary provider's discretion depending on the presence of fevers, toxemia, and the extent of soft tissue involvement. Patients will also have repeated screening for colonization including nares, throat, groin, axilla, and perirectal swabs (5 total swabs) at this time. CD4 counts and an HIV viral load will be obtained at the time of the soft tissue infection or with any MRSA infection for patients presenting to the enrolling site. Patients with positive wound culture and/or blood cultures for MRSA will be classified as a "MRSA infection." Those with a soft tissue infection without positive cultures from these sites will be classified as a "Soft Tissue Infection NOS." The patient will be treated with intravenous or oral antibiotics and/or surgical procedures at the discretion of the medical provider that the patient presents to for evaluation. Patients who have an infection while located remotely from the HIV clinic will be given a contact information card and will be asked to call the site PI or study coordinator at their enrolling site to notify them of the infection. The site PI or study coordinator will try to arrange for the aforementioned tests to be performed at the local medical clinic; CD4 counts and HIV viral loads will not be performed for patients presenting remotely to the enrolling site. In addition, coordinators will gather information on the tests and treatments performed. Patient questionnaires will be completed for patients experiencing a soft tissue infection or MRSA infection (refer to case report forms).

Patients experiencing an infection will be offered decolonization medications based on their most recent randomization assignment; those previously randomized will be maintained in their group, while those experiencing a soft tissue infection and having a positive colonization culture for the first time will be randomized to either mupirocin (Bactroban®) nasal ointment twice daily for seven days and hexachlorophene (pHisoHex®) washes with showering once daily for seven days or to a placebo nasal ointment (white petroleum) and a placebo soap with no antimicrobial activity for seven days. Patients with a positive soft tissue culture but no positive swabs from the nares, throat, groin, axilla, or perirectal areas, will not be randomized. If the primary clinician caring for a patient who experienced a MRSA infection desires to decolonize a patient regardless of the patient's randomization group, this is permitted, but must be documented and these participants will be removed from the "placebo group" for the analysis.

All cultures (from colonization sampling, wound and blood cultures) which are positive for MRSA or MSSA at the local medical treatment facilities laboratories will be preserved by freezing the isolates at -70 degrees C; these samples will be batched (isolates will be held at the primary facility and sent on a periodic basis) and sent overnight with dry ice to the NMCSD. This site will collect the specimens and send them to the laboratory at SAMMC which will perform testing on the isolates for confirmation of MRSA, antibiotic susceptibility testing (including mupirocin), and molecular analysis (to include multilocus sequence testing, PVL PCR, and other virulence factors). Some local laboratories (e.g. NMCSD) are also performing susceptibility testing on the isolates; this information will be collected if available. SAMMC will also repeat all susceptibility testing on all isolates at their facility. All samples sent to the laboratory at SAMMC will be labeled only with a PIN number of the patient. The staff at the SAMMC laboratory will not have access to personal identifiers and will have no way of linking their results to a patient name. Results

will be reported to the study lead PI using this unique identifier, together with a SAMMC-assigned identifier. These data will be utilized to characterize the MRSA isolates colonizing and infecting HIV patients, understanding the relationship between colonizing and infection-related isolates, and to determine if HIV patients acquire new strains or remain colonized with the same strain over time.

The primary endpoint of the study is the effectiveness of decolonization procedures with application hexachlorophene (pHisoHex®) soaps and nasal mupirocin (Bactroban®) compared to placebo among patients found to be colonized with MRSA in the prevention of future colonization with MRSA. As a secondary part of the study's objectives, we will also examine the effectiveness of these decolonization procedures on infections with MRSA and on soft tissue infections.

The following assessments will be performed:

a. Clinical (Visits 1, 2, 3, 4, 5, unscheduled visits)

1. Informed Consent (visit 1 only)
2. Patient Questionnaires regarding medical history, medication use, and potential risk factors for MRSA
3. Demographics (visit 1 only)
4. Review of patients medical record by study coordinators
5. Study medication dispensing (unscheduled visits for positive MRSA colonization only)
6. Adverse event review (unscheduled visits in which patient receives a study medication only)
7. Medication adherence questionnaire (visit following decolonization therapy)

b. Laboratory Values (Visits 1, 2, 3, 4, 5, unscheduled visits)

1. Swabs for MRSA colonization of the nares, throat, groin, axilla, and perirectal areas (5 swabs)
2. Pregnancy test (visit 1; visits for MRSA colonization before decolonization medications are prescribed for women of childbearing age)
3. CD4 count and HIV viral load (MRSA or soft tissue infection visit only)
4. Blood cultures (two sets) at the physician's discretion (MRSA or soft tissue infection visit only)
5. Wound culture (MRSA or soft tissue infection visit only)

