6.4 Details of Laboratory Studies

Testing

Swabs for MRSA:	Patients will have their nares, throat, groin, axilla, and perirectal areas swabbed for MRSA colonization and these swabs will be sent to the microbiology laboratory at the clinical site for determination of the presence of MRSA or MSSA at each of these sites. The laboratory will provide culture results within 3-4 days of swab collection.
Wound and blood cultures:	Patients with an active skin or soft tissue infection will have a culture of the wound performed and sent to the microbiology laboratory of the clinical site for determination of the presence of MRSA or MSSA at each of these sites. Blood cultures may be ordered based on the discretion of the primary physician.
HIV studies:	CD4 count by flow cytometry and HIV viral load will be performed at each clinical site's lab.
Pregnancy test:	Women of childbearing age will have a pregnancy test at baseline to assure she meets inclusion/exclusion criteria. This test will be repeated if she is found to be colonized with MRSA before dispensing the decolonization medications; if she is found to have a positive pregnancy test, her study participation will be terminated.

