APPENDIX D: SCHEDULE OF EVENTS

Event	Visit 1	Visit 2	Visit 3	Visit 4	Visit 5	Positive MRSA Colonization visit	MRSA Colonization Follow-up visit	MRSA/Soft Tissue Infection Visit	Additional / Unscheduled Visit
Study Month (Window: months)	0	6 (±2)	12 (±2)	18 (±2)	24 (±2)				
Informed Consent	X								
Inclusion/Exclusion Criteria	X								
Urine Pregnancy Test for women of childbearing age	X					X [#]		X [#]	
Enrollment	X								
Questionnaires including Medical History, Medications and MRSA Risk Factors	X	X	X	X	X	X		X	
Demographics	X								
MRSA Swabs for Colonization	X	X	X	X	X		X	X	
Randomization*						X		***	
Dispense Drug*						X		***	
AE Review***							X		X
Drug Accountability							X		
CD4 count/HIV Viral Load**								X	
Wound Culture and possibly blood cultures****								X	
Study Completion					X				

[#]Pregnancy test will only be performed at the MRSA colonization and infection visits among women who found to be colonized with MRSA; those with a positive pregnancy test will not receive the study medications and will be terminated from the study.

*Randomization into the mupirocin (Bactroban®) and hexachlorophene (pHisoHex®) soaps or to the placebo arm will only occur if a patient has a positive colonization swab for MRSA. Patients will be randomized in a 1:1 double-blinded fashion into these groups. Patients with colonization, regardless of the group assigned, will have repeat swabs for MRSA performed monthly (+/- 7 days) for six consecutive months. For patients with repeat positive MRSA colonization swabs on the 6-month visits, will be re-randomized during each of these events.

**AE review will occur among patients given mupirocin (Bactroban®) and hexachlorophene (pHisoHex®) or the placebo ointment and soap. AE's will be assessed that are temporally associated with study medications.

***Patients who are also found to have positive colonization swabs in addition to an infection will be randomized to one of the two treatment groups if this patient was not already randomized and the same procedures for a positive colonization visit will be followed.

****Patients presenting with a soft tissue infection will have wound cultures obtained if possible. Blood cultures also may be obtained at the primary treating physician's discretion

XVIII. ATTACHMENTS

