patients will receive a medication information sheet recommending the avoidance of applying hexachlorophene (pHisoHex®) to areas of abraded skin. This medication is category C in pregnancy as large doses of hexachlorophene (pHisoHex®) given orally and intravaginally have proven embryotoxic and teratogenic in animal studies. Although there have been inadequate studies in humans, one retrospective review found an increased incidence of fetal malformations and minor deformities of children born to nurses washing their hands with hexachlorophene (pHisoHex®) 10-60 times daily [38, 44]. The risk of toxicity in this study is low since the soap will be only used once daily for seven days among patients found to carry MRSA. All females who become pregnant or plan on becoming pregnant will be excluded from this study.

The placebo ointment which is a white petroleum jelly may cause local reactions, such as burning, stinging, soreness and pruritis. The placebo body soap will not have an antibacterial properties; it may cause a local skin reaction such as dermatitis.

The risk of phlebotomy is excess bleeding, bruising, discomfort at the site of puncture, infection, and rarely “fainting” (vasovagal syncope). Phlebotomy is generally considered a minimal risk procedure. Blood draws will be obtained at the same time that laboratories ordered by the patient’s primary physician are drawn when possible. Patients will be closely monitored and have access to medical care 24 hours a day through the emergency room and Infectious Disease clinic.

18.C.7 Benefits

The benefit of the study includes the possibility of detecting MRSA colonization and clearing it to prevent infections from this organism. The risks of blood draws and topical mupirocin (Bactroban®) and hexachlorophen (pHisoHex®) soap or placebo ointment and soap are low. A study establishing guidelines on screening and decolonization of MRSA among HIV patients could lead to better healthcare and fewer soft tissue and MRSA infections in this population.

18.C.8 Informed Consent

A model informed consent form will be provided to each investigator. If the model informed consent is modified, a copy of the modified form must be provided to the Sponsor by the investigator for approval prior to submission to the IRB or EC. The final informed consent form must be approved by the IRB or EC.

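### Section 6.3 states no positive-swab condition for re-dosing an already-randomized patient at an infection visit, and the repeat pregnancy test is tied to the swab rather than to dispensing (minor)

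*Combined protocol and SAP*

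**What the plan says.** The relevant rules stand in five places in the combined protocol and SAP.

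- **Section 6.3, paragraph on patients with an infection.** The opening rule is "Patients experiencing an infection will be offered decolonization medications based on their most recent randomization assignment". Patients already randomized keep their arm. A positive colonization culture is named only for patients being randomized for the first time. The next sentence bars patients with a positive wound culture but no positive swab from randomization; it does not mention re-dosing.
- **Section 6.3, assessment list.** Clinical item 5 reads "Study medication dispensing (unscheduled visits for positive MRSA colonization only". Laboratory item 2 places the repeat pregnancy test at "visits for MRSA colonization before decolonization medications are prescribed for women of childbearing age".
- **Section 6.4.** On the pregnancy test: "This test will be repeated if she is found to be colonized with MRSA before dispensing the decolonization medications".
- **Appendix D.** Footnote # reads "Pregnancy test will only be performed at the MRSA colonization and infection visits among women who found to be colonized with MRSA". Footnote ***, which marks the randomization and dispensing cells of the infection-visit column, says that a swab-positive patient with an infection "will be randomized to one of the two treatment groups if this patient was not already randomized".
- **Attachment C, 18.C.6.** On hexachlorophene: "This medication is category C in pregnancy". It calls the toxicity risk in this study low because "the soap will be only used once daily for seven days among patients found to carry MRSA".

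Section 6.3 also has all five colonization swabs repeated when a patient presents with an infection, so a current swab result is normally obtained.

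**The concern.** The infection paragraph works as an offer rule, and for an already-randomized patient the only stated triggers are the infection and the last assignment. The assessment list makes positive colonization the sole trigger for dispensing. Two sites could therefore handle the same swab-negative patient differently, and one of them could give hexachlorophene and mupirocin to someone who is not carrying MRSA at that visit.

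The safety side is the pregnancy test. Pregnancy is an exclusion (section 5.4) and a reason for termination (section 6.10), and the protocol guards against exposure with a test before study drug is given. That test is keyed to colonization. If drug can be given without a positive swab, the safeguard does not follow the drug.

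**Working it through.** The plan gives no figure on this point. The check is a comparison of rules, followed by a rough count of the patients concerned.

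**Rules side by side.** Take a woman of childbearing age who was randomized earlier, has an infection now, and whose swabs at this visit are negative.

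| Place | Study drug? | Pregnancy test? |
|---|---|---|
| 6.3, infection paragraph | Offered, last assigned arm | Not mentioned |
| 6.3, assessment list | No: positive colonization only | No: colonization visits |
| 6.4 | Not addressed | Only if colonized |
| Appendix D, footnote *** | No provision: swab-positive and not yet randomized | - |
| Appendix D, footnote # | - | Only if colonized |

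Section 6.3 also requires a test before these medications are dispensed, but in the paragraph on patients with a positive colonization culture. Section 6.7 likewise starts from patients found colonized. Followed literally, the infection paragraph offers her the drug and no other text triggers a test.

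**Inputs from section VII.** 50-55 participants randomized, so 25 to 27.5 per arm. MRSA infections at 13 to 40 per 1000 person-years. Planning infection rates from 5% treated and 15% placebo up to 10% treated and 38% placebo. Colonization cleared in 61-93% on mupirocin; 85% on placebo stayed colonized, so 15% cleared.

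**Assumptions.** The swab-negative share at an infection visit equals the cleared share and is unrelated to infection. Women are 5-20% of participants; the documents give no share.

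**MRSA infections among randomized patients, cited incidence.**
- Six months: 50 x 0.5 x 0.013 = 0.33 to 55 x 0.5 x 0.040 = 1.1.
- Two years: 50 x 2 x 0.013 = 1.3 to 55 x 2 x 0.040 = 4.4.

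**Infected and swab-negative, cited incidence.**
- Six months: 25 x 0.0065 x (0.61 + 0.15) = 0.12 to 27.5 x 0.020 x (0.93 + 0.15) = 0.59.
- Two years: 25 x 0.026 x 0.76 = 0.49 to 27.5 x 0.080 x 1.08 = 2.38.

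**Infected and swab-negative, planning rates.**
- Active: 25 x 0.05 x 0.61 = 0.76 to 27.5 x 0.10 x 0.93 = 2.56.
- Placebo: 25 x 0.15 x 0.15 = 0.56 to 27.5 x 0.38 x 0.15 = 1.57.
- Total: 1.3 to 4.1.

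**Women.** Lowest case 0.12 x 0.05 = 0.006; highest case 4.125 x 0.20 = 0.83. Only the active arm receives hexachlorophene, so the highest exposed figure is 2.56 x 0.20 = 0.51.

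The cited incidence counts MRSA infections only. Soft tissue infections without a positive culture fall under the same paragraph and would add to it. If infected patients carry MRSA more often than others, the swab-negative counts fall.

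**The case against.** The best defense is that the rules can be read together. The infection paragraph would say which arm a patient stays in, and the assessment list would say when drug may be dispensed. On that reading no swab-negative patient is dosed and no pregnancy test is missed. The wording helps: describing the other group as culture-positive for the first time can imply that those previously randomized are culture-positive again. Section 18.C.6 also describes the medications as being for colonized patients. The requirement in section 6.3 to test before dispensing could be applied generally by a careful site.

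Much of this stands. A reader might infer that the protocol flatly contradicts itself or deliberately doses non-carriers. The documents do not support that: the infection paragraph omits the swab condition and does not waive it. What remains is that the paragraph is worded as an offer of medication, attaches the culture condition to one group only, and bars swab-negative patients from randomization without addressing re-dosing. The restrictive wording of footnote # also works against treating the pregnancy test as general.

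The harm must be kept in proportion too. Section 18.C.6 bases the pregnancy category on large oral and intravaginal doses in animals, although it also mentions a retrospective review in nurses with very frequent hand washing. Women are tested at baseline, and those who intend pregnancy are excluded.

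**Conclusion.** The point holds as a missing condition, and its severity is minor. On its literal reading, the infection paragraph of section 6.3 is inconsistent with the dispensing item later in that section, and footnote *** makes no provision for the re-dosing. A swab-negative woman dosed on that reading would have no pregnancy test triggered.

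Fewer than one woman is expected in this position, and about 0.5 at most in the active arm. These ceilings rest on the assumed 5-20% share of women and on planning infection rates that section VII itself says may exceed those in HIV patients. They count women of any age and include no probability of pregnancy, so the expected number of exposed pregnancies is lower still.

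A reader might also infer that the extra courses threaten the efficacy result. With so few patients, the planned contrast of 85% against 23% still colonized would not be overturned, and no change to the primary comparison is claimed.

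**What to change.** 1. **Tie the pregnancy test to the drug.** In laboratory item 2 of the section 6.3 list, in section 6.4 and in Appendix D footnote #, require a negative urine pregnancy test for women of childbearing age before any dispensing of study drug, including at infection visits and whatever the swab result. Appendix D already has the test in the infection-visit column, so the cost is an occasional extra urine test.
2. **State the re-dosing rule.** In the infection paragraph of section 6.3, the sponsor should say whether an already-randomized patient needs a current positive swab to receive another course. The dispensing item and 18.C.6 suggest that one is needed. Clinical item 5 and footnote *** should then be aligned with the answer, including what an already-randomized patient receives.

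The second step is partly a design choice. If the swab condition is adopted, patients wait 3-4 days for the culture and swab-negative patients get no repeat course. Patients seen away from the enrolling clinic, for whom section 6.3 promises only an attempt to arrange swabs, may wait longer. If it is not adopted, item 5 and footnote *** must be widened, and the first step becomes essential.
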